	
ischemic ECG changes or new LBBB, but death occurred before cardiac biomarkers were obtained, or before cardiac biomarker values would be increased.
 
• Percutaneous coronary intervention (PCI) related MI is arbitrarily defined by elevation of cTn values ($>5 \times 99\text{th percentile URL}$) in patients with normal baseline values ($\leq 99\text{th percentile URL}$) or a rise of cTn values $>20\%$ if the baseline values are elevated and are stable or falling. In addition, either (i) symptoms suggestive of myocardial ischemia or (ii) new ischemic ECG changes or (iii) angiographic findings consistent with a procedural complication or (iv) imaging demonstration of new loss of viable myocardium or new regional wall motion abnormality are required.• Stent thrombosis associated with MI when detected by coronary angiography or autopsy in the setting of myocardial ischemia and with a rise and/or fall of cardiac biomarker values with at least one value above the 99th percentile URL.• Coronary artery bypass grafting (CABG) related MI is arbitrarily defined by elevation of cardiac biomarker values ($>10 \times 99\text{th percentile URL}$) in patients with normal baseline cTn values ($\leq 99\text{th percentile URL}$). In addition, either (i) new pathological Q waves or new LBBB, or (ii) angiographic documented new graft or new native coronary artery occlusion, or (iii) imaging evidence of new loss of viable myocardium or new regional wall motion abnormality. 
Criteria for prior myocardial infarction
 
Any one of the following criteria meets the diagnosis for prior MI:
 
• Pathological Q waves with or without symptoms in the absence of non-ischemic causes.

RESOLUTE ONYX Post-Approval Study Statistical Analysis Plan

10 October, 2021

Revision 7.0

Page 15 of 32

Form

Medtronic

Term	Definition								
	
 • Imaging evidence of a region of loss of viable myocardium that is thinned and fails to contract, in the absence of a non-ischemic cause. • Pathological findings of a prior MI. 								
Procedure success	Attainment of < 50 % residual stenosis of the target lesion and no in-hospital MACE.								
Stent thrombosis	
All stent thrombosis data will be reported per the Academic Research Consortium (ARC) definition:
 
Stent thrombosis should be reported as a cumulative value over time and at the various individual time points as specified below. Time 0 is defined as the time point after the guiding catheter has been removed and the subject has left the catheterization lab.
 
Timing
 
  
 Acute stent thrombosis *	0 – 24 hours post stent implantation	
 
 Subacute stent thrombosis *	> 24 hours – 30 days post stent implantation	
 
 Late stent thrombosis	> 30 days – 1 year post stent implantation	
 
 Very late stent thrombosis	> 1 year post stent implantation	
  
 
* Acute or subacute stent thrombosis can also be replaced by the term early stent thrombosis.
 
Categories of evidence
 
 1. Definite (either by angiographic or pathologic confirmation): 
 a. Angiographic confirmation of stent thrombosis is considered to have occurred if: 
 i. Thrombolysis In Myocardial Infarction (TIMI) flow is: 
 1. TIMI flow grade 0 with occlusion originating in the stent or in the segment 5mm proximal or distal to the stent region in the presence of a thrombus 2. TIMI flow grade 1, 2, or 3 originating in the stent or in the segment 5mm proximal or distal to the stent region in the presence of a thrombus ii. AND at least one of the following criteria has been fulfilled within a 48-hour time window: 
 1. New onset of ischemic symptoms at rest (typical chest pain with duration >20 minutes) 2. New ischemic ECG changes suggestive of acute ischemia 3. Typical rise and fall in cardiac biomarkers (refer to definition non-procedural related MI). 	Acute stent thrombosis *	0 – 24 hours post stent implantation	Subacute stent thrombosis *	> 24 hours – 30 days post stent implantation	Late stent thrombosis	> 30 days – 1 year post stent implantation	Very late stent thrombosis	> 1 year post stent implantation
Acute stent thrombosis *	0 – 24 hours post stent implantation								
Subacute stent thrombosis *	> 24 hours – 30 days post stent implantation								
Late stent thrombosis	> 30 days – 1 year post stent implantation								
Very late stent thrombosis	> 1 year post stent implantation								

RESOLUTE ONYX Post-Approval Study Statistical Analysis Plan

10 October, 2021

Revision 7.0

Page 16 of 32

Form

Medtronic

Term	Definition
	
Note: The incidental angiographic documentation of stent occlusion in the absence of clinical signs or symptoms is not considered a confirmed stent thrombosis (silent occlusion).
 
b. Pathologic confirmation of stent thrombosis: Evidence of recent thrombus within the stent determined at autopsy or via examination of tissue retrieved following thrombectomy.
 
2. Probable: Clinical definition of probable stent thrombosis is considered to have occurred after intracoronary stenting in the following cases:
 
a. Any unexplained death within the first 30 days.
 
b. Irrespective of the time after the index procedure any myocardial infarction (MI), which is related to documented acute ischemia in the territory of the implanted stent without angiographic confirmation of stent thrombosis and in the absence of any other obvious cause.
 
3. Possible: Clinical definition of possible stent thrombosis is considered to have occurred with any unexplained death from 30 days following intracoronary stenting until end of study follow- up.

Stroke	Sudden onset of vertigo, numbness, dysphasia, weakness, visual field defects, dysarthria or other focal neurological deficits due to vascular lesions of the brain such as hemorrhage, embolism, thrombosis, or rupturing aneurysm, that persists more than 24 hours.
Target lesion	Any lesion treated or attempted to be treated during the study procedure with the Resolute Onyx™ Stent. The target lesion is the treated segment starting 5 mm proximal to the stent and ending 5 mm distal to the stent.
Target lesion failure (TLF)	Cardiac death, target vessel myocardial infarction (Q wave and non-Q wave), or clinically driven target lesion revascularization (TLR) by percutaneous or surgical methods.
Target lesion revascularization (TLR)	Repeat PCI or CABG to the target lesion. See also clinically driven target lesion revascularization.
Target vessel	
The arterial segment and any branches and/or parent vessel that possess the target lesion.
 
Note: Side branches less than 2.0 mm in diameter will not be considered 'significant' and therefore the disease in these vessels will not be considered significant.
 
Note: Grafts to the parent vessel will be treated as side branches to that vessel for Inclusion/Exclusion Criteria evaluation, and for event evaluation and reporting – such as TV related MI and TV Revasc assessments.

Term	Definition
Target vessel failure (TVF)	
The composite endpoint comprised of cardiac death, target vessel myocardial infarction, or clinically-driven target vessel revascularization by percutaneous or surgical methods. Target vessel failure will be reported when ANY of the following events occur:
 
 • Recurrent MI occurs in territory not clearly attributed to a vessel other than the target vessel. • Cardiac death not clearly due to a non-target vessel endpoint. • Target vessel revascularization is determined.
Thrombus (intracoronary)	
Non-occlusive thrombus: Intracoronary thrombus is defined as a (spheric, ovoid or irregular) non-calcified filling defect or lucency surrounded by contrast material (on three sides or within a coronary stenosis) seen in multiple projections, or persistence of contrast material within the lumen, or a visible embolization of intraluminal material downstream.
 
Occlusive thrombus: TIMI 0 or TIMI 1 intra-stent or proximal to a stent up to the most adjacent proximal side branch or main branch (if originating from the side branch).

Total occlusion	
A lesion with no flow (TIMI 0). Total occlusions are usually classified as persisting less than or more than 3 months (chronic total occlusion).

Transient ischemic attack (TIA)	
A focal neurological abnormality of sudden onset and brief duration (lasting less than 24 hours) that reflect dysfunction in the distribution of the effected artery. TIAs include transient monocular blindness (e.g., amaurosis fugax defined as a transient episode of monocular blindness, or partial blindness, lasting ten minutes or less) and transient hemispheric attacks.

3. Introduction

This document outlines the detailed statistical methods to be implemented for the data collected within the scope of the RESOLUTE ONYX Post-Approval Study: A Post-Approval Study of the Medtronic Resolute Onyx™ Zotarolimus-Eluting Coronary Stent System. The purpose of this plan is to provide a framework within which answers to the study objectives can be achieved in a statistically rigorous fashion, without bias or analytical deficiencies. Specifically, the plan has the following purpose: To prospectively outline the types of analyses and presentations of data that will form the basis for conclusions to be reached that will answer the study objectives outlined in the protocol, and to explain in detail how the data will be handled and analyzed, adhering to commonly accepted standards and practices of biostatistical analysis in the medical device industry. Results obtained from the analyses outlined in this document will be the basis of the Clinical Study Report for this study.

4. Study Objectives

The primary objective of this study is to continue the assessment of the safety and efficacy of the Resolute Onyx™ stent for the treatment of lesions in coronary arteries amenable to treatment with a Resolute Onyx™ 2.0 mm – 5.0 mm stent.

The Bifurcation Cohort will assess the safety and efficacy of the Resolute Onyx Stent for the treatment of bifurcation lesions in native coronary arteries amenable to the treatment with Resolute Onyx Stent sizes of 2.0 – 5.0 mm utilizing the provisional stenting technique.

5. Investigation Plan

This study is designed as a single-arm, open-label multi-center study.

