 - In absence of CK: a (post PCI) rise in CKMB within 24 hours of the index event >3*URL and >50% above the previous level **or**
 - In absence of CK and CKMB: a (post PCI) rise of Troponin within 24 hours of the index event >3*URL and > 50% above the previous level
- B. If elevated CK (or CKMB) following the index MI has peaked AND CK level has returned < URL then any new rise in:
- CK >2*URL (confirmed by either CKMB > URL or Troponin >URL) **or**
 - in the absence of CK: CKMB > 3*URL **or**
 - in the absence of CK and CKMB, Troponin > 3*URL
- C. If CK (or CKMB) following the index MI has peaked AND CK level has NOT returned to < URL:
- A rise in CK >50% above the previous level and > 2*URL confirmed by either CKMB > URL or Troponin > URL **or**
 - In absence of CK, when CKMB has NOT returned < URL, a rise in CKMB >50% above the previous level and > 3*URL **or**
 - In absence of CK, when CKMB and Troponin has not returned < URL a rise in Troponin > 50% above the previous level and >3*URL

SPONTANEOUS MI >48 HOURS (PCI)

- A. Recurrent thoracic chest pain or ischemic equivalent **AND**
- New pathologic q waves in ≥ 2 contiguous ECG leads AND any CKMB > 1*URL **or**
 - in the absence of CKMB: Troponin > 1*URL **or**
 - in the absence of CKMB and Troponin: CK > 1*URL **or**
 - in the absence of CKMB and Troponin and CK: CEC decision upon clinical scenario **or**
- B. Appropriate cardiac enzyme data (respecting top-down hierarchy):
- b1. CK $\geq 2^*$ URL Confirmed by:
- CKMB > 1*URL **or**
 - in the absence of CKMB: Troponin > 1*URL **or**
 - in the absence of CKMB and Troponin: CEC decision upon clinical scenario **or**
- b2. In the absence of CK: CKMB > 3*URL **or**

Term	Definition

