Myocardial infarction (MI) Medtronic Extended Historical	
All myocardial infarction data will be reported per Medtronic Extended historical protocol definitions.
 
Medtronic Historical Definition of Q wave MI (QWMI): will require one of the following criteria:
 
 • Chest pain or other acute symptoms consistent with myocardial ischemia and new pathological Q waves in two or more contiguous ECG leads as determined by an ECG core laboratory or independent review of the CEC, in the absence of timely cardiac enzyme data. • New pathologic Q waves in two or more contiguous ECG leads as determined by an ECG core laboratory or independent review of the CEC and elevation of cardiac enzymes. In the absence of ECG data, the CEC may adjudicate Q wave MI based on the scenario and appropriate cardiac enzyme data. 
Medtronic Historical Definition of Non-Q Wave MI (NQWMI):
 
 • elevated CK $\geq 2X$ the laboratory upper limit of normal with the presence of an elevated CK-MB (any amount above the laboratory upper limit of normal) in the absence of new pathological Q waves. 
I. PCI (PERCUTANEOUS CORONARY INTERVENTION)
 
Ia. Baseline Biomarkers of Myocardial Damage (CK and CKMB and Troponin < 1*URL) and not acute MI in progress.
 
Periprocedural <48 Hours Post PCI
 
A. New pathologic q waves in ≥ 2 contiguous ECG leads AND:

RESOLUTE ONYX Post-Approval Study Statistical Analysis Plan

10 October, 2021

Revision 7.0

Page 10 of 32

Form

Medtronic

Term	Definition

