	
 ▪ in the absence of CK and CKMB, Troponin > 3*URL 
C. If CK (or CKMB) following the index MI has peaked AND CK level has NOT returned to < URL:
 
 ▪ A rise in CK >50% above the previous level and > 2*URL confirmed by either CKMB > URL or Troponin > URL or ▪ In absence of CK, when CKMB has NOT returned < URL, a rise in CKMB >50% above the previous level and > 3*URL or ▪ In absence of CK, when CKMB and Troponin has not returned < URL a rise in Troponin > 50% above the previous level and >3*URL 
Spontaneous MI >48 hours (PCI)
 
A. Recurrent thoracic chest pain or ischemic equivalent AND
 
 ▪ New pathologic q waves in \geq 2 contiguous ECG leads AND any CKMB > 1*URL or ▪ in the absence of CKMB: Troponin > 1*URL or ▪ in the absence of CKMB and Troponin: CK > 1*URL or ▪ in the absence of CKMB and Troponin and CK: CEC decision upon clinical scenario 
B. Appropriate cardiac enzyme data (respecting top-down hierarchy):
 
b1. CK \geq 2* URL Confirmed by:
 
 ▪ CKMB > 1*URL or ▪ in the absence of CKMB: Troponin > 1*URL or ▪ in the absence of CKMB and Troponin: CEC decision upon clinical scenario or 
b2. In the absence of CK: CKMB > 3*URL or
 
b3. In the absence of CK and CKMB: Troponin > 3*URL or
 
b4. In the absence of CK, CK-MB and Troponin, clinical decision based upon clinical scenario.
 
IIa. Baseline Biomarkers of Myocardial Damage (CK and CKMB and Trop < 1*URL) and not acute MI in progress.
 
Periprocedural <72 hours post CABG
 
A. New pathologic q waves in \geq 2 contiguous ECG leads or recurrent signs or symptoms consistent with myocardial ischemia AND
 
 ▪ CK-MB >5*URL or ▪ in the absence of CKMB: Troponin > 5*URL or ▪ in the absence of CKMB and Troponin: CK > 5*URL or

RESOLUTE ONYX Post-Approval Study Statistical Analysis Plan

10 October, 2021

Revision 7.0

Page 12 of 32

Form

Medtronic

Term	Definition

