7.9.2 Analysis of Secondary Endpoints

Descriptive statistics for the secondary endpoints will be provided. Categorical variables will be reported using counts and percentages, and continuous variables will be reported by giving the number of known values, the mean, standard deviation, minimum and maximum values. The time-to-event response variable may be presented by using the Kaplan-Meier methods. For the myocardial infarctions (MI) component of the endpoints, the extended historical MI definitions will be used if no specification. Results for the components of composite endpoints will be tabulated.

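### In the spontaneous-MI rule (criterion A) the new-Q-wave condition is printed only for CK-MB, so a late symptomatic event with marginal troponin can be an MI or not depending on whether CK-MB was drawn.

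*SAP*

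**What the plan says.** The spontaneous-MI rule stands in the protocol Glossary (section 2) and in SAP section 2, under the Extended Historical definition. It has two routes.

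- **Route A** opens with symptoms only: "A. Recurrent thoracic chest pain or ischemic equivalent AND". The first bullet asks for new Q waves together with raised CK-MB. It reads "contiguous ECG leads AND any CKMB > 1*URL or" in the SAP and "contiguous ECG leads AND any CKMB > 1*URL" in the protocol. The next bullets are "in the absence of CKMB: Troponin > 1*URL or" and "in the absence of CKMB and Troponin: CK > 1*URL or", and the last leaves the case to the CEC when no marker is available. None of these later bullets mentions Q waves.
- **Route B** is the enzyme route and has no symptom requirement. If CK is available, it must reach 2xURL with confirmation by CK-MB (or by troponin if CK-MB is absent). The next step is "b2. In the absence of CK: CKMB > 3*URL or", followed by b3, which takes troponin above 3xURL when CK and CK-MB are both absent.

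The periprocedural PCI criterion (Ia.A) uses the same marker sequence, but its stem ends "contiguous ECG leads AND" and all four marker bullets sit beneath it.

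On use, the same entry applies this definition to all MI data, and SAP 7.9.2 says that for the MI component of endpoints "the extended historical MI definitions will be used if no specification".

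**The concern.** An endpoint rule should give the same answer for the same event whichever assay the hospital happened to run. Here the ECG requirement applies if CK-MB was drawn and disappears if it was not.

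The plan does not control that choice for late events. Table 2 of the protocol schedules biomarkers only around the index procedure, and even there it accepts CK-MB, troponin or both. Section 10.2 asks for whatever biomarker values exist when an MI is suspected, but prescribes no assay.

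The endpoints exposed are target vessel MI, cardiac death and target vessel MI, MACE, TLF and TVF through 36 months, wherever they are reported under the Extended Historical definition. Testing practice may differ between sites and regions, so assay-driven differences could also enter the site and US/EU comparisons in SAP 7.3.

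**Working it through.** The plan states no figure on this point, so the check is one of logic. Routes A and B were written as rules from SAP section 2, with the top-down marker order. They were then applied to a symptomatic event more than 48 hours after PCI, not after CABG, with troponin at 1.2xURL. CK took the values not drawn, 0.8, 1.5 and 2.5xURL; CK-MB took not drawn, 0.8, 1.5 and 3.5xURL; new Q waves were absent or present. That gives 4 x 4 x 2 = 32 cases.

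**Text as printed, no new Q waves (16 cases)**

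| CK (xURL) | CK-MB not drawn | CK-MB 0.8 | CK-MB 1.5 | CK-MB 3.5 |
|---|---|---|---|---|
| not drawn | MI by A * | no | no | MI by B |
| 0.8 | MI by A * | no | no | no |
| 1.5 | MI by A * | no | no | no |
| 2.5 | MI by A and B | no | MI by B | MI by B |

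\* Not an MI if the Q-wave condition is moved to the stem, as in Ia.A.

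1. With CK-MB not drawn, the troponin bullet of A makes the event an MI at every CK value.
2. With CK-MB drawn at 1.5xURL and CK absent or below 2xURL, A fails for want of Q waves and B fails on its thresholds. The event is not an MI, although the CK-MB is itself raised.
3. Moving Q waves to the stem changes 3 of the 32 cases, the three marked above. None of the 16 cases with Q waves changes.
4. Some dependence on CK-MB remains after the move: a normal CK-MB still overrides a raised troponin. That is the ordinary marker hierarchy, which Ia shares, and is not the defect.

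**Comparison with the rest of the entry**

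- *Route B.* For a symptomatic event with troponin only, A already accepts anything above 1xURL, so the 3xURL threshold in b3 never decides the case.
- *Parent definitions.* The entry opens with two headings. Q-wave MI needs new Q waves, with CEC discretion when ECG data are missing. Non-Q-wave MI needs CK of at least twice the upper limit with raised CK-MB. An event with an ECG, no new Q waves, troponin at 1.2xURL and CK below 2xURL fits neither.
- *Both documents.* The protocol and the SAP print the same layout, so this is unlikely to come from PDF extraction.

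**The case against.** The strongest reply is that the intended meaning is clear enough. Substituting troponin when CK-MB is absent can be read as replacing only the CK-MB term within a Q-wave route, exactly as in Ia.A, with route B serving as the enzyme route. The parent definitions support that reading. Protocol 13.1 also has the CEC set explicit classification rules at study onset and keep its procedures in a separate manual, so bullets need not be applied mechanically.

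Much of this stands as evidence of intent. It does not repair the text: the bullets do not carry the condition, neither document states that it carries over, and the manual is not among the documents. Two adjudicators could reasonably differ.

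Two supporting arguments have limits. b3 is not dead text, because route B has no symptom requirement and b3 still governs events without symptoms. The parent definitions are not decisive either, since b2 and b3 already extend the non-Q-wave heading to cases where CK is missing. They do so, however, at a higher threshold than A.

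A reader might go further, assume a proportion of such events, add it to the planned rates of 11.3% and 16.3%, and report lost power. The documents do not support that. They give no frequency for these events and no share without CK-MB, and an event that also leads to clinically driven revascularization or cardiac death already counts in the composite. The planned rates also already contain 3.31 and 3.3 points for third UDMI (SAP 6.1 and 6.3), under which symptoms with a rise or fall and one troponin above the 99th percentile suffice without Q waves. If third UDMI drives the primary endpoints, this rule does not touch them. If Extended Historical does, the bases without that uplift are 7.95% and 13.0%. Even an assumed 2 extra points, giving 9.95% and 15.0%, leaves exact power of 99.6% (369 subjects, at most 52 events) and 93.8% (180 subjects, at most 34 events), above the planned 96% and 85%.

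**Conclusion.** The rule is wrong as written in both documents and should be corrected. The fault is confined to non-CABG events more than 48 hours after PCI with symptoms, no new Q waves, troponin just above 1xURL, and route B not met (CK not at 2xURL or more with confirmation; if CK is absent, CK-MB not above 3xURL). For those events MI status turns on whether CK-MB was drawn.

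It reaches the MI-containing endpoints reported under the Extended Historical definition. It reaches the 12-month primary endpoints only if that definition, and not third UDMI, drives them; the documents point both ways on that, which is a separate question. The effect cannot be quantified from the documents, and no claim about power follows.

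Two further inferences should be avoided. Not every MI after 48 hours passes through this branch, because MI within 72 hours of CABG has its own criteria (IIa and IIb). And the protocol's joining word before B, missing in the SAP, carries no weight: Ia lacks it in both documents, yet A and B are plainly alternatives there.

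**What to change.** In the protocol Glossary and SAP section 2, reconcile spontaneous criterion A with Ia.A and the parent definitions, so that the Q-wave condition applies identically whichever marker is available. The structure of the documents points to placing it in the stem, after the symptom requirement and ahead of all the marker bullets. If the sponsor instead intended symptoms with a marker above 1xURL to suffice without Q waves, that must be stated for CK-MB too and squared with b3 and the parent definitions.

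Align the wording with the CEC manual. Have the CEC check adjudicated MIs after 48 hours that were accepted under A on troponin or CK alone without new Q waves.

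The cost is one sentence in each document and a targeted re-read of late MIs already adjudicated. No new data are needed.
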